The two clinical studies enrolled a total of 152 patients, 102 of whom had disease refractory to at least one prior systemic therapy, 90 with advanced disease and 12 with early disease. This is the patient population for whom Targretin® capsules are indicated. Patients were initially treated with a starting dose of 650 mg/m²/day with a subsequent reduction of starting dose to 500 mg/m²/day. Neither of these starting doses were tolerated, and the starting dose was then reduced to 300 mg/m²/day. If, however, a patient on 300 mg/m²/day of Targretin® capsules showed no response after eight or more weeks of therapy, the dose could be increased to 400 mg/m²/day. Tumor response was assessed in both studies by observation of up to five baseline defined index lesions using a Composite Assessment of Index Lesion Disease Severity (CA). This endpoint was based on a summation of the grades, for all indexes lesions, of erythema, scaling, plaque elevation, hypopigmentation or hyperpigmentation, and area of involvement. Also considered in response assessment was the presence or absence of cutaneous tumors and extracutaneous disease manifestations.

All tumor responses required confirmation over at least two assessments separated by at least four weeks. A partial response was defined as an improvement of at least 50% in the index lesions without worsening, or development of new cutaneous tumors or non-cutaneous manifestations. A complete clinical response required complete disappearance of all manifestations of disease, but did not require confirmation by biopsy.

At the initial dose of 300 mg/m²/day, 1/62 (1.6%) of patients had a complete clinical tumor response and 19/62 (30%) of patients had a partial tumor response. The rate of relapse (25% increase in CA or worsening of other aspects of disease) in the 20 patients who had a tumor response was 6/20 (30%) over a median duration of observation of 21 weeks, and the median duration of tumor response had not been reached. Responses were seen as early as 4 weeks and new responses continued to be seen at later visits.

**Memorial Sloan-Kettering Cancer Center
IRB Protocol**

IRB#: 05-098 A(6)

Targretin® capsules are supplied as 75-mg off-white, oblong soft gelatin capsules, imprinted with “Targretin,” in high density polyethylene bottles with child-resistant closures.

Bottles of 100 capsules..... NDC 64365-502-01

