Responses will be determined by the criteria described in the table below. Progression of disease while on treatment should be confirmed by a second assessment 1-4 weeks later so that patients who experience a temporary flare of disease due to skin infection or other intercurrent illnesses are not removed from the study prematurely.

Assessment	Description	Status
Completely clear	No evidence of disease; 100% improvement	CCR
Marked Improvement	Greater than or equal to 50% decrease in skin scores compared to baseline and improvement is maintained for 4 weeks	PR
Slight Improvement	Less than 50% decrease in skin scores compared to baseline	SD
Worse	$\geq 25\%$ increase in skin scores compared to baseline while the patient is actively taking the study drug or $\geq 50\%$ increase in the sum of the products of the greatest diameters of pathologically positive lymph nodes (should be documented by biopsy) compared to baseline while the patient is actively taking the study drug.	PD

Assessment of Overall Skin Disease

Pruritus Relief (Appendix 1)

The intensity of pruritus will be evaluated by the patient at baseline, at the week 16 (end of treatment with Doxil®) and week 32 (after 16 weeks of treatment with Targretin®) using a 1-10 point scale, where 0 is no pruritus and 10 is the worst imaginable pruritus. A 3-point decrease in pruritus intensity confirmed by a second assessment at least 4 weeks later without an increase in the use of anti-pruritic medications is considered clinically significant in those whose pruritus score is ≥ 3 on the 0-10 point scale at baseline.

4. As a secondary goal, index lesion severity will be evaluated by a modified Composite Assessment Scale (Appendix 2). These are measurements of skin disease that have been employed and validated in the phase II-III studies of Targretin® and in the current MSKCC trial of Targretin® of Intron-A® (IRB #01-128) in CTCL. Up to 4 index skin lesions will be chosen from representative patch, plaque and tumor lesions, and erythrodermic lesions. For erythrodermic patients, a 10x10 cm. area, easily identified by anatomic landmarks will be chosen and assessed by the same scale. These index lesions will be photographed and assessed at the same time as the SWAT assessment.

In the Phase II-III studies of Targretin capsules in CTCL, the Composite Assessment (CA) of Index Lesion Disease Severity was based on a core element of the summation of index lesion

**Memorial Sloan-Kettering Cancer Center
IRB Protocol**

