
IRB#: 05-098 A(6)

clinical signs . Up to a maximum of five (5) cutaneous T-cell lymphoma lesions were designated as index lesions. If the patient had five or fewer CTCL lesions, then all CTCL lesions were designated as index lesions. If the patients had more than five CTCL lesions, then five lesions that were representative of the patient's overall cutaneous disease were designated as index lesions. The index lesions were preferably separate and distinct from other lesions in order to minimize the chance of lesion confluence. Individual index lesion clinical signs and symptoms were to have been graded at each visit according to a 0-to-8 point scale (see Table). A CA summation was generated by summing the grades for each index lesion for each clinical sign. To determine the area of each index lesion, the longest diameter and the longest diameter perpendicular to this diameter of each index lesion were to have been measured to the nearest millimeter. The area in square centimeters was then converted to a 0-to-18 scale in order to provide a means for integrating the area into the CA summation of grades (see Table). The summation of CA grades at baseline was divided into the summation of CA grades at each subsequent post-baseline study visit to determine the CA ratio to provide an objective measure of the patient's response to treatment (e.g., a CA ratio <1.0 indicated improvement in disease and a ratio >1.0 indicated a worsening of disease). This CA score was found to correlate with the Physicians Global Assessment, which is replaced by SWAT in this study.

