* For scaling and erythema, intermediate intervals 1, 3, 5 and 7 were to serve as mid-points between the defined grades 0, 2, 4, 6 and 8.

**Memorial Sloan-Kettering Cancer Center
IRB Protocol**

IRB#: 05-098 A(6)

Table Grading Scales for Composite Assessment (CA)
of Index Lesion Disease Severity (continued)

Page 2 of 2

HYPO-/HYPER-PIGMENTATION	
To have been used only when hypopigmentation or hyperpigmentation was the clinical manifestation of CTCL.
 
0 - No evidence of pigmentation change.
 
1*
 
2 - Mild: 25% lighter pigmentation or noticeably darker pigmentation compared to the patient's normal skin pigmentation.
 
3*
 
4 - Moderate: 50% lighter pigmentation or twice as dark pigmentation compared to the patient's normal skin pigmentation.
 
5*
 
6 - Severe: 75% lighter pigmentation or three times as dark pigmentation compared to the patient's normal skin pigmentation.
 
7*
 
8 - Very severe: Nearly complete absence of pigmentation or nearly as dark a pigmentation as could be observed compared to the patient's normal skin pigmentation.

--------------------------	---

* Intermediate intervals 1,3,5 and 7 are to serve as mid-points between the defined grades 0, 2, 4, 6 and 8.

INDEX LESION AREA	
0 - 0 cm² (no measurable area)
 
1 - > 0 and ≤ 4 cm²
 
2 - > 4 and ≤ 10 cm²
 
3 - >10 and ≤ 16 cm²
 
4 - >16 and ≤ 25 cm²
 
5 - >25 and ≤ 35 cm²
 
6 - >35 and ≤ 45 cm²
 
7 - >45 and ≤ 55 cm²
 
8 - > 55 and ≤ 70 cm²
 
9 - >70 and ≤ 90 cm²
 
10 - >90 and ≤ 110 cm²
 
11 - >110 and ≤ 130 cm²
 
12 - >130 and ≤ 155 cm²
 
13 - >155 and ≤ 180 cm²
 
14 - >180 and ≤ 210 cm²
 
15 - >210 and ≤ 240 cm²
 
16 - >240 and ≤ 270 cm²
 
17 - >270 and ≤ 300 cm²
 
18 - >300 cm²

-------------------	--

**Memorial Sloan-Kettering Cancer Center
IRB Protocol**

IRB#: 05-098 A(6)

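### For erythrodermic patients, a fixed 10x10 cm square scored on a scale that grades area adds an unchanging 10 points while diffuse disease fills it, which damps the secondary Composite Assessment ratio

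*Combined protocol and SAP*

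**What the plan says.** Section 12.7, item 4, of the combined protocol and SAP sets the CA as a secondary goal, using up to four index lesions. Erythrodermic patients get a special rule: "For erythrodermic patients, a 10x10 cm. area, easily identified by anatomic landmarks will be chosen and assessed by the same scale".

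The same section then describes the CA as used in the earlier bexarotene studies. Signs were scored as follows: "Individual index lesion clinical signs and symptoms were to have been graded at each visit according to a 0-to-8 point scale (see Table". Lesion size came from two diameters: "the longest diameter and the longest diameter perpendicular to this diameter of each index lesion were to have been measured to the nearest millimeter". Size then entered the score: "The area in square centimeters was then converted to a 0-to-18 scale in order to provide a means for integrating the area into the CA" sum. The sum at each visit was divided by the baseline sum to give the CA ratio, with values below 1 meaning improvement.

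Appendix 2 gives the grading tables. Scaling, erythema and elevation run from 0 to 8, and a pigmentation grade of 0 to 8 is used only where pigment change is how the disease shows itself. Area runs from 0 to 18. The band containing 100 cm² is "10 - >90 and ≤ 110 cm²" and the lowest is "0 - 0 cm² (no measurable area").

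The scale is called modified. Apart from the maximum of four lesions (five in the earlier studies) and the square itself, no modification is described. Nothing says that the area grade is dropped, held fixed or redefined for the square.

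**The concern.** The area term was built for lesions with their own edges, which can shrink under treatment or grow with progression. A square placed by anatomic landmarks has edges chosen by the assessor. Its size carries no information about disease, yet the instruction to use the same scale brings the area grade with it. A number that cannot move is then added to both the numerator and the denominator of the ratio, which pulls the ratio toward 1.

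At stake is the meaning of a declared secondary measure in one subgroup. Both improvement and worsening would look smaller in erythrodermic patients than the graded signs show. A CA ratio from such a patient would also not be comparable with one from a patient with discrete lesions. These patients are expected in the trial: Section 6.1 makes provision for erythroderma-Sézary syndrome (T4).

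**Working it through.** The plan states no figure that depends on this point, so there is none to reproduce first.

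**Inputs**
- Size of the square: 10 × 10 = 100 cm² (Section 12.7, item 4).
- Area grade for 100 cm²: A = 10 (Appendix 2, band above 90 and up to 110 cm²).
- Sign grades: 0 to 8 each for scaling, erythema and elevation, so the baseline sign sum S is at most 3 × 8 = 24, or 4 × 8 = 32 if pigmentation applies.
- CA ratio: sum at the visit divided by sum at baseline (Section 12.7, account of the earlier studies). I assume that this trial forms the same ratio.
- S itself is not in the documents. A range is shown.
- The square is taken as the patient's only index area.

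**Formula.** If the signs fall by a fraction f and the area grade stays at 10,

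CA ratio = (S(1 − f) + 10) / (S + 10).

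The improvement shown is 1 − ratio = fS/(S + 10). On the signs alone it would be f. The share hidden is therefore 1 − S/(S + 10) = 10/(S + 10), whatever f is. The same share applies when the signs worsen.

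**Results**

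| S | Share hidden, 10/(S+10) | Ratio when all signs are halved (signs alone: 0.50) |
|---|---|---|
| 6 | 10/16 = 62.5% | 13/16 = 0.81 |
| 10 | 10/20 = 50% | 15/20 = 0.75 |
| 12 | 10/22 = 45% | 16/22 = 0.73 |
| 20 | 10/30 = 33% | 20/30 = 0.67 |
| 24 | 10/34 = 29% | 22/34 = 0.65 |
| 32 | 10/42 = 24% | 26/42 = 0.62 |

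**If involved skin inside the square is graded instead.** Take signs falling from 12 to 6, with a baseline sum of 12 + 10 = 22:
- 100 cm² still involved (grade 10): 16/22 = 0.73.
- 50 cm² involved (grade 7): 13/22 = 0.59.
- 25 cm² involved (grade 4): 10/22 = 0.45.

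Where clearing is patchy, the two ways of scoring the same patient can thus differ by 0.73 − 0.45 = 0.28. Where the square stays fully involved, they agree at 0.73.

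**The case against.** **The constant is only one reading.** Area was measured from lesion diameters, and Appendix 2 has a grade for no measurable area. An assessor could therefore grade the involved skin inside the square. This stands for patchy clearing, and it limits the claim to visits at which diffuse disease fills the square. It also rules out a tempting inference, that the ratio can never reach 0 after full clearing: the lowest area grade is available once nothing measurable remains. It does not remove the point, because the protocol does not tell the sites of a multi-center trial which reading applies.

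**Damping is part of the CA.** Any lesion that fades without shrinking is damped. With signs going from 12 to 6, an unchanged lesion above 300 cm² (grade 18) gives 24/30 = 0.80, more damped than the square. That is correct. The difference is that a discrete lesion can shrink, whereas the outer size of the square cannot.

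**Most of the improvement hidden?** A reader might infer this. It holds only if S is below 10. At S = 12 and S = 24 the share is 45% and 29%, and the documents give no baseline grades to settle which applies.

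**Missed responses?** A reader might also take a CA ratio of 0.50 as a threshold that these patients would fail to reach. The criterion "A partial response was defined as an improvement of at least 50% in the index lesions" in Section 5.0 describes the earlier bexarotene studies. In this trial the 50% rule applies to SWAT skin scores, and no CA cut-off is set.

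**Pooling.** Neither Section 2.0 nor Section 14.0 mentions the CA, so no pooled CA analysis is specified. The number of erythrodermic patients among the 37 is not given either. Distortion of a pooled result is a possibility, not a planned error.

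**Conclusion.** The point holds as a limited flaw in a secondary measure. Followed as written, Section 12.7, item 4, scores a landmark-fixed square on a scale that grades area, which adds 10 points at baseline and at each visit while diffuse disease fills the square. The CA ratio then hides 10/(S + 10) of any change in the signs, from about 62% at S = 6 to 29% at S = 24.

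This rests on three assumptions: the range taken for S, the use of the ratio described for the earlier studies, and scoring of the size of the square as opposed to the involved skin within it.

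A reader might infer an effect on the trial's main conclusions. The documents do not support that. Section 12.7 gives dermatologic response to SWAT, and Section 14.0 bases the primary endpoint on progression-free status at 12 months. CR, PR, SD and PD assignments do not depend on the CA. This is a cheap improvement, not a threat to the trial.

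**What to change.** Add one sentence to Section 12.7, item 4, and to Appendix 2: for the 10x10 cm erythrodermic square, the Index Lesion Area grade is left out of the CA sum at baseline and at all later visits, so that the ratio uses the sign grades only. A halving of the signs then gives a ratio of 0.50 at every S. Add one line stating that CA results are reported separately for erythrodermic and discrete-lesion patients.

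This needs no new measurements, and existing results can be recalculated if the component grades were recorded separately. There are two small costs. The erythrodermic CA departs from the scale used in the earlier studies, and it no longer reflects patchy clearing inside the square. Both can be covered by also reporting the full CA with area defined as the involved skin within the square. That supplementary version requires the involved area to be recorded at each assessment.

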13.0 CRITERIA FOR REMOVAL FROM STUDY

If at anytime the patient develops progressive disease he/she will be taken off study and referred for alternative therapy.

If at anytime the patient develops unacceptable toxicity he/she will be removed from study. If

at anytime the patient is found to be ineligible for the protocol as designated in the section on Criteria for Patient/Subject Eligibility (i.e., a change in diagnosis), the patient will be removed from the study.

14.0 BIOSTATISTICS

This is a phase II, multi-center, open-label, single arm trial. The goal of this trial is to improve response rate and prolong progression-free survival in patients with cutaneous T-cell lymphomas with the sequential use of Targretin® after an optimal course of Doxil®. The primary endpoint is progression-free survival at 12 months. Based on historical data, the median progression-free is 12 months for treatment of CTCL with Doxil®. With the new treatment, this trial will be considered as promising if the probability of progression-free at 12 months is 70%. Thirty seven patients are needed in this trial with conventional type I error 0.05 and power 0.8. This trial would be considered to be promising for further study if 24 or more patients are progression free at one year. There is 80% chance of observing 24 or more progression-free out of 37 patients if the true rate is 70% or better.

**Memorial Sloan-Kettering Cancer Center
IRB Protocol**

IRB#: 05-098 A(6)

The second endpoints are complete response and partial response rates.

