7.0 RECRUITMENT PLAN

The trial will require 37 patients to meet study endpoints. With the targeted annual accrual of 10-15 patients, this study will require about 3 years to complete accrual.

Potential research subjects will be identified by a member of the patient's treatment team, the protocol investigator, or research team at Memorial Sloan-Kettering Cancer Center (MSKCC-Lead Center), M. D. Anderson Cancer Center, New York University Medical Center, Hackensack University Medical Center, and Roswell Park Cancer Institute. If the investigator is a member of the treatment team, s/he will screen their patient's medical records for suitable research study participants and discuss the study and their potential for enrolling in the research study. Potential subjects contacted by their treating physician will be referred to the investigator/research staff of the study.

Consent Process

Participation is voluntary. The patient must be aware of the nature of his/her disease and willingly consent after being informed of the procedures to be followed, the experimental nature of the therapy, alternatives, potential benefits, side effects, risks and discomforts. All patients will be required to sign a statement of informed consent that conforms to IRB guidelines. Informed consent will be documented by the use of a written consent form that has been approved by the institution's IRB. Three copies of the informed consent will be signed and dated by the patient or the patient's legally authorized representative. One copy will be given to the patient, one copy will be filed in the patient's medical record, and one copy will be retained in the Protocol Participant Registration (PPR) Office. Written consent will be obtained by either the principal investigators or participating investigators.

Memorial Sloan-Kettering Cancer Center
IRB Protocol

IRB#: 05-098 A(6)

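### Section 14 has no rule to stop accrual once 14 failures put 24 of 37 out of reach; adding one leaves type I error and power unchanged

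*Combined protocol and SAP*

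**What the plan says.** Section 14.0 defines the endpoint as a yes/no outcome at one time point: "The primary endpoint is progression-free survival at 12 months". The sample size is given as "Thirty seven patients are needed in this trial with conventional type I error 0.05 and power 0.8", and the decision rule is "This trial would be considered to be promising for further study if 24 or more patients are progression free at one year". The reference point is a historical median: "Based on historical data, the median progression-free is 12 months for treatment of CTCL with Doxil". The design target is a 12-month rate of 70%, and the stated power is "There is 80% chance of observing 24 or more progression-free out of 37 patients if the true rate is 70% or better".

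Section 7.0 plans for all 37 patients: "With the targeted annual accrual of 10-15 patients, this study will require about 3 years to complete accrual".

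No section gives an interim look, a futility boundary or a condition for closing accrual. Section 13.0 deals only with taking individual patients off study. Section 16.1 has accrual and follow-up checked periodically. Section 16.2 refers to institutional monitoring procedures to be set at activation. Neither states an efficacy or futility criterion.

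**The concern.** The outcome takes up to 12 months to observe and accrual is expected to take about three years, so many failures will be known while enrolment is still open. If the regimen does no better than the historical rate or does worse, the 14th failure can arrive before the 37th patient is registered. Every patient enrolled after that receives a cytotoxic drug followed by a retinoid in a trial that can no longer meet its own criterion.

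Most futility rules cost some power. Stopping only when success has become arithmetically impossible costs none, so the usual reason for leaving such a rule out does not apply.

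**Working it through.** **Inputs.** N = 37, success threshold 24, alpha 0.05, power 0.80 and target rate 0.70 are from Section 14.0. The null rate of 0.50 is not written as a rate; it is implied by the 12-month historical median. Accrual of 10 to 15 a year is from Section 7.0.

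**Step 1: reproduce the plan's figures.** With X the number progression-free at 12 months, X ~ Binomial(37, p):

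- Type I error: P(X ≥ 24 | p = 0.50) = 0.0494.
- Power: P(X ≥ 24 | p = 0.70) = 0.8071.

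Both agree with the stated 0.05 and 0.8. The sidedness of alpha is not stated, but the one-sided reading reproduces N: 37 with threshold 24 is the smallest exact one-sided design that meets both limits.

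**Step 2: the point of no return.** Failures allowed = 37 − 24 = 13. After a 14th, the most successes possible is 37 − 14 = 23, which is below 24.

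**Step 3: effect on error rates.** If 14 of the 37 have finally failed, the full trial ends as not promising whatever happens to the rest. A trial stopped there reaches the same conclusion, so the two designs never disagree. Type I error stays 0.0494 and power 0.8071. The decisions also matched in every simulated trial.

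**Step 4: how many patients are spared.** This depends on how fast failures become known, so it needs assumptions. All rows below use exponential progression-free survival set to a true 12-month rate of 50%, no loss to follow-up, and accrual closed at the 14th known failure. Arrivals are even, except in the last row, where they are random (Poisson). Paired values are for 10 and 15 patients a year.

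| When a failure is known | Accrual stops early | Mean enrolled | Mean spared (37 − mean) |
|---|---|---|---|
| At once | 81% / 69% | 31.3 / 33.0 | 5.7 / 4.0 |
| At weeks 16, 32, 45 or 52, plus 2.5 weeks for confirmation | 71% / 50% | 32.8 / 34.8 | 4.2 / 2.2 |
| As above, plus one month to report | 66% / 41% | 33.4 / 35.4 | 3.6 / 1.6 |
| Only at month 12 | 43% / 16% | 35.1 / 36.5 | 1.9 / 0.5 |

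The week-16 and week-32 assessments approximate Appendix 3. The later times approximate Section 10.6, which asks for visits at least every three months. The 2.5 weeks is the middle of the 1 to 4 weeks that Section 12.7 gives for confirming progression on treatment. The one-month reporting lag is an assumption.

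**Step 5: other true rates**, from immediate detection down to scheduled detection with the reporting lag:

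- 40%: about 4 to 10 spared.
- 30%: about 7 to 13 spared (3.1 to 7.1 if failures are learned only at month 12).
- 70%: almost none, at most about 0.2.

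**Step 6: shape of the curve.** If failures come later in the year (Weibull, shape 2), the saving at 50% is smaller: 2.3 to 4.0 with immediate detection and random arrivals. With even arrivals, scheduled detection and the reporting lag it is about 0.8 at 15 a year. The shape changes only the number spared.

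**The case against.** The strongest reply is that nothing here is wrong. The single-stage design is coherent, meets its stated error rates and contradicts no other section. That stands: this is an improvement to offer, with no error to correct.

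Three stronger readings are tempting, and the documents do not support them.

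- *That the protocol requires enrolment to continue after the verdict is fixed.* It is silent. Sections 16.1 and 16.2 leave room for the study team or the institutional committee to act, and the activation-stage procedures are not in the documents. What can be said is that no written criterion would trigger a stop.
- *That the stop would usually fall within accrual if the regimen is no better than the null.* That is so with immediate detection. Skin scoring is scheduled only around weeks 16 and 32 after baseline, progression on treatment should be confirmed, and Section 16.0 has sites send forms bimonthly. At 15 a year with those delays, fewer than half of trials stop early. In the other direction, patients are examined every two weeks on Doxil and regularly on Targretin, so some progression will be noticed between scheduled assessments.
- *That one bare sentence about 14 failures is enough.* The no-cost property needs failures that cannot be undone. Section 14.0 does not say how deaths, toxicity removals or losses before 12 months count. Section 13.0 removes patients found ineligible without saying whether they stay in the 37. The progression criteria in Section 12.7 are tied to active study treatment. If a counted failure were later excluded, replaced or not confirmed, accrual could close while 24 was still reachable.

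Response rate is a stated secondary objective, and early closure makes that estimate less precise. This cost is real, but it arises only in a trial that has already missed its primary criterion.

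**Conclusion.** The point holds as an omission with a cheap remedy. The threshold of 14 and the unchanged error rates are arithmetic. They rest on no assumption about the survival curve, only on the 14 being final failures within the 37-patient denominator. The figure 0.0494 also takes the implied null rate of 50%.

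The benefit is modest and uncertain. At a true rate of 50%, between about 0.5 and 6 patients are spared on average, depending on accrual and on how soon progression is known; about 1.5 to 4 is a reasonable working range. The saving grows as the regimen performs worse and nearly vanishes at 70%, so the rule would seldom touch a trial of a regimen that works. These counts rest on the exponential shape, accrual of 10 to 15 a year and no loss to follow-up.

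**What to change.** Add to Section 14.0 wording such as: *Accrual stops when 14 patients in the primary-analysis denominator have final failures (progression confirmed as in Section 12, or death, within 12 months), since 24 of 37 can no longer be reached; patients already enrolled continue as planned.*

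In the same paragraph, state how patients removed for toxicity, lost before 12 months or later found ineligible count in the 37, whether any are replaced, and how progression off study drug is recorded. The final analysis needs these definitions in any case.

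No accrual pause, alpha adjustment or larger sample is needed. The running cost is a count of confirmed failures at the coordinating center, which already registers every patient centrally (Section 15.1), with prompt reporting of progression by the sites. The price is a less precise response-rate estimate when the stop is triggered.
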